## **4 Study Objectives and Endpoints**

### **4.1 Objectives**

#### **4.1.1 Primary objectives**

- Evaluate the frequency of dose reductions in two different lenalidomide dose regimens.

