### 10.3 Statistical Methodology

Each treatment arm will be further stratified into those patients who received a reduction in dosage level and those who did not. As a first step, potential differences among the four groups on demographic variables will be tested. Those variables that are categorical will be analyzed by Chi Sq.; those variables that are quantitative will be analyzed by two-way between-groups Analyses of Variance. Any variable where a significant difference is established will be controlled by entry into future analyses as covariates.

The primary outcome variable is the proportion of patients in each treatment arm that received any dosage reduction, independent of when in the course of treatment this reduction occurred or how many subsequent reductions were introduced. These data will be analyzed by logistic regression with treatment arm as the main predictor and any variables found significant in the first step entered as covariates. A secondary analysis will consider the rate at which any dose reductions were introduced. For example, it is possible that the proportion of patients that receive a dose reduction may be equivalent in the two treatment arms, but that those patients in one arm may have received their reductions earlier. This will be examined by a Cox Proportional Hazard test, and, if necessary, with the same covariates identified above.

Power analysis shows that with a total N = 80 (40/group) power = .80 to detect an effect size difference in proportions of 32% (p=.05, 2-tail) (Borenstein M, Rothstein H and Cohen J. Power and Precision (2004). Englewood, NJ, Biostat).

This sample size provides adequate power to observe similar difference in dose reduction between the two groups for a range of dose reductions (10% - 40%) in 15mg dose group.

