#### **10.5 Sample size and power considerations**

Assume the dose reduction rate for 25 mg arm is 50%, a sample size of 80 subjects (40 per arm) will provide a power of 81.6% to detect a difference of 30% (the rate of dose reduction assumed to be 20%) at significance level of 0.05.

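### The trial is sized on a difference in dose-reduction proportions, but section 10.3 plans neither that difference nor a confidence interval for the primary outcome

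*Combined protocol and SAP*

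**What the plan says.** The primary objective in section 4.1.1 is "Evaluate the frequency of dose reductions in two different lenalidomide dose regimens". Section 10.3 turns this into a variable: "The primary outcome variable is the proportion of patients in each treatment arm that received any dosage reduction". (Section 4.2.1 lists adverse events as the primary endpoint. That is a separate matter, and this point follows 10.3.)

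The one analysis named for this variable is in 10.3: "These data will be analyzed by logistic regression with treatment arm as the main predictor", with "any variables found significant in the first step entered as covariates". The first step tests demographic variables across four groups formed by arm and by whether the dose was reduced. The Cox model that follows is labelled secondary.

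The sizing is on the scale of proportions. Section 10.3 quotes power of .80 for a 32-point difference with 40 per group. Section 10.5 begins "Assume the dose reduction rate for 25 mg arm is 50" per cent, takes the other rate as "the rate of dose reduction assumed to be 20" per cent, and says that 40 per arm "will provide a power of 81.6% to detect a difference of 30" per cent.

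For secondary outcomes, 10.3 does plan intervals: a one-sided 95% lower limit for the response rate and 90% CIs for the marker proportions. It plans none for the primary outcome.

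**The concern.** The design question is how many percentage points separate the two arms. The analysis answers with a model coefficient on another scale. An odds ratio converts to a difference only once a base rate is fixed. It is also non-collapsible: with the same two arm rates, the odds ratio conditional on a prognostic covariate lies further from 1 than the unadjusted one, even when the covariate is perfectly balanced. Because the covariates are chosen after the data are in, the quantity that the odds ratio estimates is not settled in advance.

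Sections 10.1 and 1 describe the aim as selecting a tolerable regimen with acceptable efficacy. Weighing tolerability against efficacy calls for the absolute change in the reduction rate and its uncertainty. As written, the report could give a significant odds ratio and two percentages and still comply with the plan. The reader would not see how wide a range of differences the data allow.

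**Working it through.** **Inputs.** Rates of 50% (25 mg) and 20% (the other arm), 40 per arm, alpha 0.05 (section 10.5); two-sided (section 10.3); 15 mg rates of 10% to 40% (section 10.3); age effect of 46% v 31% (section 3.3). Covariate strengths other than age are assumptions.

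**1. The plan's own figure.** Two-sided comparison of two proportions, pooled variance under the null:

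- pooled rate = 0.35; SE0 = √(2 × 0.35 × 0.65 / 40) = 0.1067
- SE1 = √((0.25 + 0.16) / 40) = 0.1012
- power = Φ((0.30 − 1.96 × 0.1067) / 0.1012) = Φ(0.90) = 81.55%, against 81.6% stated

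Exact enumeration of the unadjusted logistic Wald test on the same design also gives 81.6%. The change of scale does not affect the test or N.

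**2. The two scales.** OR = (0.5/0.5) / (0.2/0.8) = 4.0. The match with 30 points holds only at a 20% base rate:

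| 15 mg rate | OR equal to 30 points | Points equal to OR 4.0 |
|---|---|---|
| 10% | 6.0 | 20.8 |
| 20% | 4.0 | 30.0 |
| 30% | 3.5 | 33.2 |
| 40% | 3.5 | 32.7 |

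**3. Effect of adjustment, documented covariate.** Age: (0.46/0.54) / (0.31/0.69) = 1.90. Take a balanced 50:50 binary covariate with that odds ratio and solve ½·expit(a) + ½·expit(a + ln 1.9) = arm rate, separately for each arm:

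- 25 mg: 42.04% and 57.96% (mean 50%)
- 15 mg: 14.96% and 25.04% (mean 20%)
- odds ratio within either stratum ≈ 4.13
- differences 27.1 and 32.9 points, mean 30.0

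The odds ratio moves from 4.0 to about 4.13 and the difference stays at 30 points. Read back at a 20% rate, 4.13 gives 30.8 points.

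**4. Effect of adjustment, assumed stronger covariates.** The same calculation gives:

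- normal covariate with OR 2.0 or 2.7 per SD: 4.58 or 5.19
- balanced binary covariate with OR 5 or 10: 4.85 or 5.90

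The difference is 30 points throughout. In simulation at 40 per arm, with binary covariate odds ratios of 1.9, 5 and 10, the difference standardised from the adjusted model averaged 29.8 to 29.9 points.

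**5. The missing output, at the planning rates (20/40 v 8/40).**

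- Wald: 0.30 ± 1.96 × 0.1012 = 10.2 to 49.8 points
- Newcombe, from Wilson limits 0.352 to 0.648 and 0.105 to 0.348: lower 0.30 − √(0.148² + 0.148²) = 9.1 points; upper 0.30 + √(0.148² + 0.095²) = 47.6 points
- logistic: SE(log OR) = √(1/20 + 1/20 + 1/8 + 1/32) = 0.506; OR 4.0, 95% CI exp(1.386 ± 1.96 × 0.506) = 1.48 to 10.8

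**The case against.** The arm proportions are the named primary outcome, so a crude difference is one subtraction away. In a 1:1 randomised trial that crude difference is a valid estimate of the planning quantity, with or without adjustment. The words odds ratio do not appear in the documents; that measure is inferred from the model. Sizing on proportions and testing by logistic regression is ordinary practice. No selection rule depends on a risk difference or a 30-point threshold. The width of 10 to 50 comes from 80 patients, not from the choice of scale. All of this stands, and it limits the point to what is not pre-specified: the difference as the estimate, and its interval.

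A reader might infer three stronger things.

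- **That the 30-point question gets no estimate at all.** The documents do not support this, since both proportions will be on the page.
- **That the trial is underpowered or wrongly sized because of the scale.** Step 1 of the working shows otherwise.
- **That the adjusted odds ratio will be badly inflated.** The one predictor whose strength is documented moves it by about 0.13. Figures such as 5.2, or its conversion to 36.5 points, need assumed stronger covariates. The conversion also applies a conditional odds ratio to a marginal rate, which the plan never proposes.

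One part of the objection shapes the remedy. Standardising from the model as planned would keep covariates screened on groups that the outcome itself helps define. In a simulation of that screening, with an assumed 3 to 6 demographic variables, the median adjusted odds ratio was about 4.4 to 4.5, the standardised difference stayed near 30 points, and 95% intervals covered about 93 to 94%. The loss is small, but it is avoidable.

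**Conclusion.** The point holds as a gap in the planned estimation. The primary outcome is a proportion and the sizing is a difference in proportions, yet the only planned between-arm result is a logistic coefficient whose meaning depends on covariates not yet chosen. No difference and no interval is planned for the primary outcome, while secondary outcomes have intervals. This is so even if no covariate enters the model.

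The consequence is moderate. The hypothesis test and N = 80 are unaffected. At the planning rates, the unplanned interval would run from about 10 to 50 points, which matters to anyone choosing between regimens. The drift in the odds ratio is secondary: about 4.0 to 4.13 for a balanced binary covariate with the strength of the documented age effect, and 4.6 to 5.2 only under assumed odds ratios of 2.0 to 2.7 per SD. These figures assume true rates of 50% and 20%, equal arms and balanced covariates.

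**What to change.** In section 10.3, keep logistic regression for the test and add that the primary estimate is the difference between arms in the proportion with any dose reduction, with a 95% CI. Name the interval method (Newcombe, for example) and report both arm proportions beside it. Report the odds ratio with its CI as supportive.

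The difference may be either:

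- crude, which is simplest and needs no covariates; or
- standardised from a logistic model (average predicted rate under each arm, with a delta-method or bootstrap interval), with baseline covariates such as age fixed in advance and not chosen by the four-group screening.

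The cost is a short addition to 10.3 and a few lines of analysis code. It needs no new data and no change in N.

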 If patient has progressive disease after 2nd cycle, then the patient will be taken off the study. If at least a minimal response (MR) has not resulted after cycle 4, then the patient will be taken off the study. Subjects who continue to show evidence of myeloma response will remain on the study and will be evaluated every 4 weeks for response/progression.

---

 All patients enrolled in the study must register through RevAssist® and must comply with all requirements of the RevAssist® program. Prescriptions must be filled within 7 days for females of childbearing potential and 14 days for all other risk categories. Drug will be shipped on a per patient basis by the contract pharmacy to the clinic site. Only enough lenalidomide for one cycle of therapy will be supplied to the patient each cycle.

 **All subjects who respond to lenalidomide plus dexamethasone may continue on therapy until there is evidence of progression or unacceptable toxicity. All subjects will be followed for survival indefinitely.**

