## 5 Investigational Plan

### 5.1 Overall design

This is a multi-center, controlled, open-label, randomized (1:1) parallel group study intended to select the dose regimen with the most promising efficacy of Lenalidomide, when used in combination with dexamethasone.

[figure not shown]
Subjects will receive either oral Lenalidomide 25 mg once daily for days 1-21 out of a 28 cycle or Lenalidomide 15 mg once daily for 1-21 of a 28 day cycle. Subjects will also receive 40 mg of dexamethasone once a week (Days 1, 8, 15 and 22) with a dose reduction on the same schedule if the patient cannot tolerate the higher dose of dexamethasone ([refer to Section 5.5.3](#)). ASA (81 or 325 mg) will be given orally for anticoagulation prophylaxis. If patient has progressive disease after 2nd cycle, then the patient will be taken off the study. If at least a minimal response (MR) has not resulted after cycle 4, then the patient will be taken off the study. Subjects who continue to show evidence of myeloma response will remain on the study and will be evaluated every 4 weeks for response/progression.

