## 5.8 Follow-Up

Subjects who discontinue treatment for any reason will not be followed. At treatment discontinuation, subjects will undergo a safety assessment approximately 28 days post the last dose of study drug. In addition, off study evaluations per the Schedule of Assessments, Section 2 will be done. All subjects who respond to treatment will be followed for survival indefinitely.

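### The primary dose-reduction proportion ignores time at risk, so unequal removal between arms can shift it in either direction

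*Combined protocol and SAP*

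**What the plan says.** Section 10.3 defines the primary outcome as the "proportion of patients in each treatment arm that received any dosage reduction, independent of when in the course of treatment this reduction occurred". On the model it says: "These data will be analyzed by logistic regression with treatment arm as the main predictor", with covariates chosen in a first step. It gives no observation window, no exposure term and no rule for patients who leave before any reduction. Whether reductions come earlier in one arm is a secondary question: "This will be examined by a Cox Proportional Hazard test", using those covariates where needed. No censoring or competing-event rule is given.

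Section 10.2 keeps every randomized patient with at least one lenalidomide dose in the analysis, so early leavers remain in the denominator.

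Three sets of rules decide how long a patient can have a reduction:

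- **Response.** Section 5.1 takes patients off study for progression after cycle 2. Footnote 10 of the Section 2 schedule repeats this and adds: "If at least a minimal response (MR) has not resulted after cycle 4, then the patient will be taken off the study". Footnote 12 lets responders stay on until progression or unacceptable toxicity, with no maximum number of cycles.
- **Toxicity.** Table 2 in Section 5.5.3 sends some events (for example grade 4 neuropathy, or a blistering rash of any grade) directly to removal, with no reduction step.
- **Other reasons.** Section 5.7 ends treatment at progression at any time, and for several further causes.

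**The concern.** Section 3.3 makes the need for dose reduction the yardstick of tolerability. A patient removed at cycle 4 for poor response, or at cycle 1 for a toxicity that bars further lenalidomide, can no longer have a reduction and is counted the same as a patient who tolerated full dose for a year. For the toxicity removals this puts the worst tolerability outcome on the favourable side of the primary comparison.

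If removal were equally common in both arms, the arms would be affected alike when their reduction risks are equal. Nothing in the plan ensures that. An arm with less disease control loses more patients at cycles 2 and 4, and its reduction proportion falls mechanically. An arm with more direct toxicity removals is flattered in the same way. Section 10.3 says the study is not powered to compare response, so a difference in response-based removal could go undetected and still move the primary result, in a trial meant to select a tolerable regimen.

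**Working it through.** **1. The plan's own figure.** Section 10.5 gives 50% against 20%, 40 per arm, significance level 0.05; Section 10.3 gives two tails. With pooled variance:

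power = Φ[(0.30 − 1.96·√(2·0.35·0.65/40)) / √((0.25 + 0.16)/40)] = Φ[(0.30 − 0.2090)/0.1012] = Φ(0.898) = 81.55%.

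The stated 81.6% reproduces. It treats each patient as one binomial trial and makes no allowance for unequal time at risk.

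**2. Response-based removal.** The documents give no removal rates, so shares and horizons here are assumptions. Take the same per-cycle risk h in both arms, set so that 50% (the Section 10.5 rate) have a reduction by cycle F: h = 1 − 0.5^(1/F). If an extra share r of one arm is removed after cycle 4, its proportion is

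p(r) = (1 − r)·0.5 + r·[1 − (1 − h)^4].

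The bracket is 1 − 0.5^(4/8) = 0.293 for F = 8 and 1 − 0.5^(4/12) = 0.206 for F = 12.

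| F | r | p(r) | Gap from 50% |
|---|---|---|---|
| 8 | 0.20 | 0.8·0.5 + 0.2·0.293 = 45.9% | 4.1 points |
| 8 | 0.40 | 0.6·0.5 + 0.4·0.293 = 41.7% | 8.3 points |
| 12 | 0.20 | 0.8·0.5 + 0.2·0.206 = 44.1% | 5.9 points |
| 12 | 0.40 | 0.6·0.5 + 0.4·0.206 = 38.3% | 11.7 points |

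The risk of reduction is identical throughout; only time at risk differs.

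**3. Direct toxicity removal.** Each patient in an arm of 40 who is removed for toxicity without a prior reduction, and so counted as not reduced rather than as an event, lowers that arm's proportion by 1/40 = 2.5 points. If such removals are commoner at 25 mg, the shift runs opposite to a response-driven shift favouring 15 mg.

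**4. The Cox analysis.** Take h = 7.5% and 12 cycles. In the 25 mg arm, remove 10% after cycle 2 and 20% after cycle 4 of those still on treatment and unreduced. Two cycles carry a risk of 1 − 0.925² = 0.1444, and the last eight 1 − 0.925^8 = 0.4640.

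- 25 mg: 0.1444 + 0.8556·0.9·0.1444 + 0.8556²·0.9·0.8·0.4640 = 50.0%.
- 15 mg, same h, removals 20% and 40%: 0.1444 + 0.8556·0.8·0.1444 + 0.8556²·0.8·0.6·0.4640 = 40.6%.
- 15 mg, same h, removals 30% and 60%: the same sum with 0.7 and 0.4 gives 32.6%.

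In 4,000 simulated trials of 40 per arm, a test of the crude proportions rejected in 14% (20%/40%) and 37% (30%/60%) instead of 5%. The log-rank test, which is the score test of an unadjusted Cox model, censored at removal, rejected in 5% of trials in both cases, with hazard ratios of 1.01 and 1.00. When removal was made likelier in patients with a low personal reduction risk (log-normal frailty, SD 1), the hazard ratios were 1.07 and 1.12, against the 15 mg arm.

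**5. What a remedy does.** Over cycles 1 and 2 alone, both arms in step 4 show 14.4%. The cumulative incidence of reduction, with removal as a competing event, gives exactly p(r) in step 2 at cycle F, since that illustration has no other censoring. It therefore keeps the same 4.1 to 11.7 point gaps.

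**The case against.** **The plan already has a time-based analysis.** This stands, and it limits the point. A reader might infer that the Cox analysis is itself faulty and would make 15 mg look better tolerated. The documents do not support that. Censored at removal, a Cox model estimates the cause-specific hazard and uses time at risk, and in step 4 any bias under dependent removal went against 15 mg. Its gaps are an unstated censoring rule and its reliance on removal being unrelated to reduction risk. It is also only secondary.

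**The direction is not known.** This also stands. A reader might conclude that the design favours 15 mg, but that requires 15 mg to be less effective, which the documents neither show nor exclude. Section 3.3 suggests that dose reduction did not harm efficacy, but it reasons from age groups in earlier trials of a 25 mg start and does not speak to starting at 15 mg. Direct toxicity removals may flatter 25 mg.

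**The crude proportion is a legitimate description.** It says how often a reduction occurs under the regimen as actually used. It does not by itself measure tolerability, which is the use made of it in Section 3.3.

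**An early window is not perfectly clean.** Section 5.7 ends treatment at progression at any time, and Sections 5.5.2 and 5.5.3 apply the reduction for most late-cycle toxicity at the start of the next cycle. Both need handling in the definition.

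**Lack of follow-up is not the issue.** Section 5.8 says: "Subjects who discontinue treatment for any reason will not be followed". A patient off lenalidomide cannot have a lenalidomide reduction, so this loses no primary outcome data.

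**Conclusion.** The point holds for the primary analysis. The crude proportion mixes reduction risk with time at risk, and it counts response-based and direct toxicity removals as not reduced. With equal reduction risk, an extra 20% to 40% removed after cycle 4 shifts the proportion by 4.1 to 11.7 points, against a design difference of 30. These sizes rest on assumed removal shares, a constant per-cycle risk and assumed horizons of 8 or 12 cycles. The shift is too small to create the whole design effect, but large enough to matter when tolerability is compared with 40 patients per arm. Its direction depends on which arm has more removal and of which kind, so no claim that one dose is favoured follows from the documents. The planned Cox analysis is a partial correction once its censoring is stated. This should be changed before analysis; it does not invalidate the trial.

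**What to change.** In Section 10.3, leaving all treatment and removal rules as they are:

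1. Add a composite of first lenalidomide reduction or lenalidomide discontinuation for toxicity, compared by arm with the same logistic and Cox models.
2. Add a fixed-window logistic analysis of reductions triggered by toxicity with onset in cycles 1 and 2, including those applied at the start of cycle 3. Note as a limitation that a few patients may leave for progression before the window closes or before a cycle 3 reduction is applied.
3. State that the Cox model is cause-specific and censored at removal for progression, for less than a minimal response, or for other non-toxicity reasons. In the model for reduction alone, toxicity removal also ends time at risk, so the composite must be read beside it. Interpret the primary proportion alongside both.
4. Report by arm the cumulative incidence of reduction, of response-based removal and of toxicity removal. Label this as description, not correction, because the incidence of reduction also falls when removal rises.

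The cost is a little extra programming on data the protocol already collects: adverse event duration and action taken (Section 6.2), diaries and capsule counts (Section 5.5.4), and response assessments (Section 2). The downside is fewer events, and so less precision, in the fixed-window analysis.

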
STUDY DESIGN:
 
This is a multi-center, controlled, open-label, randomized (1:1) parallel group study intended to select a tolerable dose regimen with acceptable efficacy of lenalidomide, when used in combination with dexamethasone.
 
Subjects will receive either oral lenalidomide 25 mg once daily for days 1-21 out of a 28 cycle or lenalidomide 15 mg once daily for 1-21 of a 28 day cycle. Subjects will be assessed before the start of treatment, and every 4 weeks while on therapy. Subjects will also receive 40 mg of dexamethasone once a week, (days 1,8,15, 22), and ASA (81 or 325 mg) will be given daily for anticoagulation prophylaxis. Lenalidomide will be reduced if patients develop grade 3 or greater toxicities. If patient has progressive disease after 2nd cycle, then the patient will be taken off the study. If at least a minimal response (MR) has not resulted after cycle 4 then the patient will be taken off the study. (see Section 5.7). Subjects who continue to show evidence of myeloma response will remain on the study and will be evaluated every 4 weeks for response and/or progression.
	

STUDY ENDPOINTS
 
Primary:
 
 
Type, frequency, severity and timing of adverse events and their relationship to combination therapy with lenalidomide plus dexamethasone
 
 
Secondary:
 
 
Duration of M-Protein response during combination therapy with lenalidomide plus dexamethasone
 
Confirmed M-Protein response
 
Expression of angiogenic factors, cytokines, adhesion molecules, and myeloma biomarker expression
 
	

STUDY DURATION: Subjects who respond to lenalidomide plus dexamethasone may continue on therapy until there is evidence of
	
TOTAL SAMPLE SIZE: Approximately 80 subjects will be enrolled.

Lenalidomide (Revlimid®)

progression or unacceptable toxicity. All subjects will be followed for survival indefinitely.
	

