## 10 Biostatistical Analysis

### 10.1 Overview

This is a multi-center, controlled, open-label, randomized, parallel group study intended to select a tolerable dose regimen with acceptable efficacy of lenalidomide, when used in combination with dexamethasone. Patients will be randomized with 1:1 ratio to receive lenalidomide 25 mg + dexamethasone or lenalidomide 15mg + dexamethasone. The primary objective of the study is to evaluate the frequency of dose reductions in two different lenalidomide dose regimens. The study will help in selecting a safe lenalidomide dose for the elderly population.

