**Secondary endpoints:** Although this study is not powered to compare response as well as duration of response to the 2 dose regimen, we will collect and analyze both using power analysis. Objective response rate is defined as the proportion of randomized subjects who have evidence of either partial response or complete response as determined using the EBMT and IMWG criteria. One-sided 95% confidence limits on the lower limit of the percentage of responders will be established to determine if this lower bound exceeds 45%. Duration of response is computed among the subgroup of subjects whose best response is PR or better. It is defined as is the time from when measurement criteria are first met for objective response until the date of progression or death. A subject with an objective response who does not have a progression event will be censored at the same time as he or she was censored under the primary definition of PFS.

The data on growth factors and other markers will be collected. For each protein, the proportion of patients who are up or down-regulated will be reported along with the 90% CI. The Fisher's exact test (two sided significance level of 5%) will be used to compare the proportions of patients with CR+PR for those who are upregulated vs. those who are down-regulated.

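### Response has no planned between-arm estimate, and its only stated criterion, a lower limit above 45%, cannot tell the two doses apart

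*Combined protocol and SAP*

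**What the plan says.** Efficacy is part of the stated purpose, in two wordings. Section 5.1 describes a study "intended to select the dose regimen with the most promising efficacy of Lenalidomide", which is comparative. The synopsis describes one "intended to select a tolerable dose regimen with acceptable efficacy of lenalidomide", and Section 10.1 repeats that aim. Section 10.1 also sets out the randomisation: "Patients will be randomized with 1:1 ratio to receive lenalidomide 25 mg + dexamethasone or lenalidomide 15mg + dexamethasone".

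The analysis of response is in the secondary-endpoint paragraph of Section 10.3. It concedes that "this study is not powered to compare response as well as duration of response to the 2 dose regimen" and continues that "we will collect and analyze both using power analysis". It then gives one criterion: "One-sided 95% confidence limits on the lower limit of the percentage of responders" "will be established to determine if this lower bound exceeds 45" percent.

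That paragraph does not say whether the limit is computed per arm or on all patients, which interval method is used, or what follows from passing or failing. It gives no between-arm difference, interval, test or margin for response. Duration of response is defined there too, also without a between-arm method. The Fisher test in the same section compares responders by direction of marker regulation, not by arm.

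**The concern.** The case for a lower dose rests on little response being lost. The synopsis and Section 3.3 argue that dose reduction did not noticeably affect outcomes in an earlier programme. How much response might be lost at 15 mg is therefore central to choosing a dose. Randomisation would allow an unbiased estimate of that loss, but the plan uses it only for dose reductions.

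With only a threshold check in the plan, a report could show one dose above 45% and the other not, and nothing beside it would say how compatible the two results are. It could equally show both doses above the threshold while leaving a large difference unreported. Each arm's result speaks to a fixed benchmark and not to the other arm.

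**Working it through.** **Inputs.** 40 patients per arm (Section 10.3: "with a total N = 80 (40/group) power = .80"); one-sided 95% limit and 45% threshold (Section 10.3). The documents assume no response rate for either arm, so a range of common true rates is shown. One value, 61%, is the lenalidomide plus dexamethasone response rate in the phase III trials described in Section 3.2.

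**The plan's own power figure.** Section 10.5 states 81.6% power for dose-reduction rates of 50% against 20%. With the pooled normal approximation, z = [0.30·√40 − 1.96·√(2·0.35·0.65)] / √(0.50·0.50 + 0.20·0.80) = (1.897 − 1.322)/0.640 = 0.90, which gives 81.55%. The figure reproduces. It concerns dose reductions; no power or error rate is stated for the 45% check.

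**Responders needed per arm.** This is the smallest count out of 40 whose one-sided 95% lower limit exceeds 45%.

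| Method | Limit at 23/40 | Limit at 24/40 |
|---|---|---|
| Clopper-Pearson | 43.3% | 45.8% |
| Wilson | 44.6% | 47.0% |
| Wald | 44.6% | 47.3% |

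All three methods need 24/40, an observed 60%. The exact chance of passing at a true 45% is 4.1%.

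**Chance that exactly one arm passes when both share the true rate p.** Let q = P(X ≥ 24) for X ~ Binomial(40, p). With independent arms, the chance of a split is 2q(1 − q).

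| Common true rate p | q | 2q(1 − q) |
|---|---|---|
| 40% | 0.008 | 1.7% |
| 45% | 0.041 | 7.8% |
| 50% | 0.134 | 23.2% |
| 55% | 0.319 | 43.4% |
| 60% | 0.568 | 49.1% |
| 61% | 0.619 | 47.2% |
| 65% | 0.798 | 32.3% |
| 70% | 0.937 | 11.9% |
| 75% | 0.988 | 2.3% |

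At 61%: both pass 0.619² = 38.3%, neither passes 0.381² = 14.5%, exactly one passes 47.2%. The split chance is at least 45% only for p from about 56% to 61.5%. With 38 or 36 evaluable per arm it is 48.2% or 49.1% at p = 61%.

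**What a split or a match can hide.** Counts of 24/40 and 23/40 split the arms, though they differ by 1/40 = 2.5 points. The simple 95% half-width for that difference is 1.96·√(0.60·0.40/40 + 0.575·0.425/40) = 21.6 points. Counts of 24/40 and 36/40 both pass, though they differ by 30 points.

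**Pooled reading.** With n = 80, 44 responders (55%) are needed; the Clopper-Pearson limit is 45.2% at 44 and 44.0% at 43. There is one result for the whole trial, so a split cannot occur, but neither dose is assessed.

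**What a between-arm estimate would deliver at 40 per arm.** The 95% half-width is 1.96·√(2p(1 − p)/40): 21.9 points at p = 50%, 21.4 at 61% and 20.1 at 70%. Against 61% in one arm, two-sided 5% power is 14% for 51% in the other, 27% for 46%, 43% for 41% and 78% for 31%.

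**The case against.** The strongest reply is that the plan never claims to compare response. It says openly that it is not powered to do so. Its primary objective, primary analysis and sample size all concern dose reductions, and a minimum-activity check suits the aim of acceptable efficacy in the synopsis and Section 10.1. This largely stands. Low power is not the defect, and no test or larger sample is called for. But lack of power is a reason to give an estimate with its interval; it does not justify giving none. Section 5.1 still states a comparative aim.

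Two stronger readings are tempting, and the documents support neither.

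- *Two equally effective doses would get opposite results almost half the time.* That holds only near a common true rate of 56% to 61.5%. The 61% is background, not a planning value. It comes from trials with dexamethasone on Days 1-4, 9-12 and 17-20 in dexamethasone-sensitive patients. Here dexamethasone is weekly, one arm starts at 15 mg, and prior lenalidomide or dexamethasone is allowed.
- *The plan ranks the doses by the 45% rule.* No section ties dose selection to passing or failing, and per-arm use, though the natural reading in a paragraph about two regimens, is not stated.

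It is also fair to say that the added interval would be too wide to settle much. It would still show which losses of response remain plausible, which the threshold check cannot.

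**Conclusion.** The point holds as a gap in the analysis plan. A randomised trial meant to select a dose partly on efficacy specifies no between-arm estimate of response. It names a method that is not one, and leaves the scope and use of its single response criterion undefined.

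The size depends on an unknown response rate. On a per-arm reading with 40 per arm, independent arms and equal true rates, a split occurs from about 8% of the time (true rate 45%) through 47% (61%) to 12% (70%). A split is therefore weak evidence of a difference between doses, and a match is not evidence of similarity. On a pooled reading the split problem disappears, but so does any information on either dose. The missing estimate matters on both readings. The change is worth making but does not affect the primary analysis.

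**What to change.** In Section 10.3, make three changes.

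1. For response, replace the reference to power analysis with: *ORR will be reported by arm in the mITT population by randomised arm, with the 25 mg minus 15 mg difference and its two-sided 95% Newcombe CI.*
2. Align the denominator. Section 10.3 defines the response rate over randomised patients, while Section 10.2 bases all analyses on those who took at least one dose of lenalidomide, classified as randomised. The two must name the same set.
3. State that the 45% check is applied to each arm separately, is descriptive, and is not evidence of a difference between doses.

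The power-analysis phrase also covers duration of response; the wording above deals with response only.

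The cost is a few sentences and one table row. Sample size, data collection and treatment do not change. The downside is that an interval of about ±21 points will show openly that similar efficacy has not been established.
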